	
H9. AGITATION
 
 (0) No evidence of fidgetiness or nervous habits
 
 (1) Fidgetiness
 
 (2) Playing with hands or hair
 
 (3) Moving about, can't sit still.
 
 (4) Repetitive and often continuous excessive motor activity, typically involving hand-wringing, nail biting, rocking, rubbing of legs, pacing, hair-pulling, lip biting, etc.
	

Total HRSD Score

--	--

SC/Rater Signature _____ Date _____

VA COOPERATIVE STUDY #556
The Effectiveness of rTMS in Depressed VA Patients

Site ____ Participant # _____ Alpha Code _____ Date ____/____/____

Form 21 - Beck Depression Inventory

Circle Visit Below:

Baseline

Acute Treatment Phase Sessions: 5 10 15 20 25 30

Follow-up Phase Weeks: 4 8 12 16 20 24

On this questionnaire are groups of statements. Please read each group of statements carefully. Then pick out the one statement in each group which best describes the way you have been feeling the PAST WEEK, INCLUDING TODAY! Circle the number beside the statement you picked. If several statements in the group seem to apply equally well, circle each one. Be sure to read all the statements in each group before making your choice.

1 0 I do not feel sad.
 1 I feel sad.
 2 I am sad all the time and I can't snap out of it.
 3 I am so sad or unhappy that I can't stand it.

2 0 I am not particularly discouraged about the future.
 1 I feel discouraged about the future.
 2 I feel I have nothing to look forward to.
 3 I feel that the future is hopeless and that things cannot improve.

3 0 I do not feel like a failure.
 1 I feel I have failed more than the average person.
 2 As I look back on my life, all I can see is a lot of failures.
 3 I feel I am a complete failure as a person.

4 0 I get as much satisfaction out of things as I used to.
 1 I don't enjoy things the way I used to.
 2 I don't get real satisfaction out of anything anymore.
 3 I am dissatisfied or bored with everything.

5 0 I don't feel particularly guilty.
1 I feel guilty a good part of the time.
2 I feel quite guilty most of the time.
3 I feel guilty all of the time.

6 0 I don't feel I am being punished.
1 I feel I may be punished.
2 I expect to be punished.
3 I feel I am being punished.

7 0 I don't feel disappointed in myself.
1 I am disappointed in myself.
2 I am disgusted with myself.
3 I hate myself.

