		Negative	Positive	No Result
1.	Methamphetamine (MET) and Ecstasy (ECS)			
2.	Amphetamine (AMP) and Methylenedioxymethamphetamine (MDA)			
3.	Marijuana (THC)			
4.	Cocaine (COC)			
5.	Opiates (OPI)*			

Dip Card B

1.	Barbiturates (BAR)*			
2.	Benzodiazepines (BZD)*			
3.	Phencyclidine (PCP)			
4.	Methadone (MTD)*			
5.	Oxycodone (OXY)*			

II. Alcohol Test

1.	Alcohol			
		Negative	Positive	No Result

* Opiates, barbiturates, benzodiazepines, methadone, and oxycodone, and THC may be positive if the patient is using these medications in accordance with a valid prescription.

VA COOPERATIVE STUDY #556
The Effectiveness of rTMS in Depressed VA Patients

Site ____ Participant # _____ Alpha Code _____ Date _____ / _____ / _____

MM DD YYYY

Form 34 – STUDY COMPLETION / TERMINATION

Complete this form when patient completes the study or when it is determined that patient will not be returning for study visits.

1. Did participant complete study? No Yes

2. Date of study termination or completion. Mo____ Day____ Yr_____

3. Major reason for not completing study?
01 = Completer - end of study
02 = Withdrew consent
03 = Moved
04 = Unable to return for appointments
05 = Incarceration
06 = Lost to follow-up, no response to contacts
07 = Deceased (Complete Adverse Event form pack) AE Reference # _____
(Date of death) Mo____ Day____ Yr_____

- 08 = Intolerance of burden of visits, interviews
09 = Administrative discharge
10 = Pregnancy
11 = Adverse medical event _____
(Complete Adverse Event form pack) AE Reference # _____

- 12 = Lack of effectiveness
13 = Other medical illness, specify _____
14 = Other psychiatric problem, specify _____
15 = Other, specify _____

4. Was care transferred to primary Psychiatrist? No Yes
4a. If No, why? _____

5. Does the participant believe that the treatment was effective in treating their depression?
(Circle One) Not at all Slightly Moderately Considerably Extremely

VA COOPERATIVE STUDY #556
The Effectiveness of rTMS in Depressed VA Patients

Site ____ Participant # _____ Alpha Code _____ Date ____/____/____

Form 35 - Control Questionnaire

Participant complete:

Before First Treatment Session After First Treatment Session End of the Study

End of the Study completed by:

Local Site Investigator TMS Treater Study Coordinator

1. Please indicate your best guess as to which treatment group the participant was assigned?

Real rTMS Sham

2. How confident are you that your guess is correct?

Extremely

Considerably

Moderately

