Slightly

Not at all

Signature _____ Date _____

Participant completed (SC sign for Participant completed form)

VA COOPERATIVE STUDY #556
The Effectiveness of rTMS in Depressed VA Patients

Site ____ Participant # _____ Alpha Code _____ Date ____/____/____

Form 36 – Protocol Deviation

Complete for each protocol deviation

1. Protocol Deviation _____

- 01 = Adverse Event not reported
- 02 = SAE/UADE not reported
- 03 = SAE/UADE reported late
- 04 = Participant not monitored for AE/SAE/UADE
- 05 = Did not follow instructions from IRB or other review bodies/committees
- 06 = Confidentiality or privacy breach
- 07 = Loss of source documents/samples/source media
- 08 = Improper enrollment of a member of a vulnerable population
- 09 = Inappropriate participant randomization
- 10 = Ineligible participant enrolled
- 11 = Pregnancy test not performed prior to enrollment of female participant
- 12 = Participant in more than one simultaneous interventional trial
- 13 = Inappropriately modified informed consent/HIPAA
- 14 = Informed Consent/HIPAA documentation completed incorrectly
- 15 = Informed Consent/HIPAA documentation is incomplete
- 16 = Informed Consent/HIPAA not obtained prior to study procedures
- 17 = Reconsent/HIPAA reauthorization not obtained in timely manner
- 18 = Used incorrect informed consent/HIPAA version
- 19 = Drug/Device accountability issue
- 20 = Inappropriate intervention unblinding
- 21 = Intervention used by non-study individual
- 22 = Performed activities not allowed by protocol
- 23 = Performed study procedure at incorrect interval
- 24 = Required study procedure not performed per protocol
- 25 = Study activities performed by inappropriate personnel
- 26 = Study intervention not administered per protocol
- 27 = Participant non-compliance

Site ____ Participant # _____ Alpha Code _____ Date MM / DD / YYYY ____

99 = Other, provide description and reason: _____

2. Date of Deviation: MM / DD / YYYY ____

3. Comment: _____

VA COOPERATIVE STUDY #556
The Effectiveness of rTMS in Depressed VA Patients

FORM 37A – ADVERSE EVENT (AE)

FOR COLLECTING ADVERSE EVENTS (AEs) AND ADVERSE DEVICE EVENTS (ADEs) DEFINED IN THE PROTOCOL

Site Participant # Alpha Code

Date of Report: (mm-dd-yyyy): - - -

1. Adverse Event (s) Being Reported (enter the diagnosis if known; otherwise enter a sign or symptom):

2. AE start date/time (record the date/time the AE began) (mm-dd-yyyy): - - -

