 - Patient should be routinely queried at each visit as to whether they have experienced any adverse events. Reports of significant, possible related adverse events such as changes in hearing or vision should prompt adverse event reporting and further evaluation to ensure that no patient is placed at excessive risk.

5. *Interruptions*

Every attempt shall be made to complete each treatment session as per the protocol. Interruptions during the treatment are allowed as needed for patient comfort or convenience by using the “pause” selection on the device. However, in the event that an incomplete treatment is given, this information will be recorded. Total number of treatments will be recorded. Since this is an “intent to treat” design, patients that miss treatments are not removed from the study. However, post-hoc analyses will examine the effects of compliance on overall outcome.

6. *Evaluations*

Patients are first tested for “remission” after the first 20 sessions of treatment and then again at the 25th and 30th sessions. Remission is defined as a decrease in Hamilton Rating Scale for Depression *to 10 or less*. If a patient enters “remission” after 20 sessions, then they enter a 24-week follow-up period. If a patient does not enter “remission” at the end of 20 sessions, they are offered an additional 5 sessions of treatment and retested for “remission.” This procedure may continue for a

maximum of 10 additional sessions resulting in a total of 30 sessions. Patients who do not show a treatment response at the end of 30 sessions of treatment or who drop out during treatment will be considered a treatment “failure”.

At the end of the acute treatment phase, all patients will be entered into a 24 week follow-up phase. Participants who remit will receive a 3 week treatment taper at the beginning of the follow-up phase. The taper will include 3 treatment sessions in the first week, 2 in the second week and 1 in the last week of the taper.

7. *Sham (Control) rTMS Treatment*

Sham (Control) treatment will be accomplished by using the Cool-B65-A/P coil that functions both as an active (A) and placebo (P) coil. It has a symmetrical mechanical design and no labeling on the coil indicates the active or placebo side. Consequently it is not possible for the operator to see or hear which side is used.

8. *Masking*

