Every attempt will be made to mask the patient and the treatment administrator to the treatment group assignment, as will all personnel at each clinical site. Each site will be supplied with 2 coils; one C-B60 coil for MT determination and one Cool-B65 A/P coil for treatment.

Additionally, for each treatment session, whether sham or active, each patient shall wear scalp electrodes through which, in the case of sham treatments, a low-voltage, low electric current (2 – 20ma at no more than 100V) will be passed in order to provide cutaneous stimulation that mimics the sensation of actual rTMS. At the same time, the Sham Noise Generator is used in order to hide the click noise. When a magnetic stimulation pulse is fired, white noise is sent to the ears of the patient. This sham noise pulse will hide the click noise from the coil for the patient. The treatment administrator also receives the sham noise.

To further assess the adequacy of the mask, rTMS administrators, clinical raters, and patients will complete a Control Questionnaire at the time of the final study visit to assess their “best guess” as to treatment condition, and their level of confidence in

this guess. Successful blinding of experienced rTMS administrators determined to break the blind with this method has been piloted by [name], and found to be successful.

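### Form 35 and Appendix K disagree on whose mask is assessed and when, and Form 35 has the coordinator, who may also rate the HRSD, sign the sheet carrying the participant's treatment guess

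*Protocol*

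**What the plan says.** **Appendix K, section 8 (Masking).** To assess the mask, "rTMS administrators, clinical raters, and patients will complete a Control Questionnaire at the time of the final study visit". Respondents give a best guess and their confidence in it. No other time point is named.

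**Form 35 (Control Questionnaire).** The participant's time points are "Before First Treatment Session After First Treatment Session End of the Study". At end of study the form is also completed by staff, with three boxes: "Local Site Investigator TMS Treater Study Coordinator". Each respondent chooses real rTMS or sham and rates confidence. Below the signature line stands "Participant completed (SC sign for Participant completed form", so the study coordinator (SC) signs the sheet on which the participant has answered.

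**Form 20 (HRSD and MADRS).** It ends with one shared line, "SC/Rater Signature". Its post-baseline visits begin at acute session 5.

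**Use of the HRSD.** Appendix K section 6 and Form 16 question 4 make an HRSD total of 10 or less the remission criterion. The result decides whether sessions continue and whether the taper begins.

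**Masking intent.** Appendix K section 3 says that the treatment administrator and everyone else on the study team are masked.

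**The concern.** A mask check serves two purposes: it should cover the people whose knowledge could bias the outcome, and it should not itself become a source of such knowledge. Form 35 is weak on both counts, in different staffing situations.

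The HRSD is clinician-rated, and parts of it rest on the rater's judgement. On Form 20, retardation and agitation are scored only from observed behaviour, and depressed mood and psychic anxiety draw on nonverbal cues. A rater who knows that the participant believes the treatment is real, or sham, may score these items with that in mind. If participants' beliefs after session 1 differ by arm, such a tendency would differ by arm too. Appendix G states that sham stimulation lacks the skin sensation of active stimulation, which is why scalp electrodes are used to mimic it. The answer given after session 1 is where imperfect mimicry would first show.

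**Working it through.** The documents give no figure to reproduce, so the check is a comparison of texts.

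**1. Respondents**

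| Role | Appendix K section 8 | Form 35 |
|---|---|---|
| Participant | yes | yes |
| rTMS administrator / treater | yes | yes |
| Clinical rater | yes | no box |
| Site investigator | not named | yes |
| Study coordinator | not named | yes |

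The two lists agree on two roles and differ on three.

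**2. Time points.** Appendix K names the final visit only. Form 35 has three participant time points, two of them around session 1.

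**3. Order relative to the ratings.** Form 20 lists post-baseline ratings at sessions 5, 10, 15, 20, 25 and 30 and at follow-up weeks 4, 8, 12, 16, 20 and 24, so up to 6 + 6 = 12 per participant. The first two guesses are on paper before all of them.

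**4. Two staffing cases**
- *The rater is not the coordinator.* The coordinator's signature does not expose the rater to the guess. But the rater has no box, so the rater guess that Appendix K promises cannot be recorded as such.
- *The rater is the coordinator.* The Study Coordinator box captures the rater's guess. But that person has already signed the sheets carrying the participant's guesses, so the rating may be coloured by them, and the rater's own end-of-study guess is partly an echo of what the participant wrote.

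**5. What the size would depend on.** Suppose a rater scores d points lower when the participant says real than when the participant says sham, and let p_A and p_S be the shares saying real in the active and sham arms. The false arm difference is d × (p_A − p_S). If guesses are correct with probability a in both arms, then p_A = a and p_S = 1 − a, which gives d × (2a − 1).
- Guess before session 1: under randomisation p_A = p_S in expectation, so the difference is 0.
- Guess after session 1, at chance (a = 0.50): 0.
- Illustration with assumed inputs only: d = 1 and a = 0.55 gives 1 × 0.10 = 0.1 HRSD points; d = 2 and a = 0.70 gives 2 × 0.40 = 0.8 points.

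Neither d nor a is in the documents, and the illustration assumes that every rater sees the form and acts on it. It shows how the bias would arise and does not estimate it.

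**The case against.** Only the forms and appendices of the protocol are available here. The main text may name a separate HRSD rater or say how Form 35 is collected, and a safeguard missing from a blank form may still exist in the protocol. This stands, and it is why the coordinator-rater overlap is put here only as a possibility. It does not remove the conflict between Form 35 and Appendix K.

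Four stronger conclusions are tempting, and the documents do not support them.

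- *That the coordinator is the HRSD rater.* An SC signature line also closes pure self-report forms such as the Beck Depression Inventory, the Beck Hopelessness Scale and the VR-36, so it looks like routine sign-off. Form 20 has a separate field for the interviewer's initials. The shared line permits the overlap but does not establish it. Nor does Form 35 say that the coordinator reads the answers.
- *That the rater is unmasked.* A participant's guess is not the allocation. The guess before session 1 carries no information on it, and the later one does so only as far as the sham can be detected. The symmetrical coil, scalp electrodes and noise generator are there to prevent that.
- *That the mask protecting the HRSD is not assessed at all.* Much of the HRSD rests on what the patient reports, so the participant's mask protects it as well, and Form 35 assesses that three times. Guesses from the treater, investigator and coordinator are also taken. A missing rater guess leaves a gap in the evidence on masking but does not bias any score.
- *That both defects apply together.* For any one rater they are alternatives.

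**Conclusion.** The conflict between Form 35 and Appendix K over who answers and when is plain on the text and needs no assumption about anyone's behaviour. Its consequence depends on staffing. With a separate rater, a promised part of the mask assessment goes unrecorded. With a rating coordinator, there is an avoidable route for expectation bias into every post-baseline HRSD, the score behind remission and the decision to continue sessions. The second consequence rests on three conditions that the available text does not settle: that the coordinator rates, that the coordinator sees the answers, and that guesses after session 1 differ by arm. If any of these fails, there is no bias between arms by this route. Its size cannot be derived from the documents. This is a cheap improvement to make, not a threat to the trial's validity.

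**What to change.** 1. Add a Clinical rater box to the staff respondents on Form 35. If the coordinator is the rater, say so in both places.
2. Align Form 35 and Appendix K section 8 on one list of respondents and one set of time points, including whether the two participant guesses around session 1 are intended.
3. Have participants seal their answers or enter them directly, with the coordinator signing for receipt only. Keep the answers closed to anyone who rates outcomes until that participant's last rating.

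The cost is one tick box, short wording changes to the form and the appendix, and minor handling work for envelopes or direct entry. It needs no added visit or staff.

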1. INTRODUCTION AND PURPOSE

Each site investigator (SI) is responsible for a complete and accurate accounting of all study devices and other materials received by the site. The VA Cooperative Studies Program Clinical Research Pharmacy Coordinating Center (PCC) in Albuquerque, New Mexico will provide instructions and assistance as necessary to assure proper use of and accountability for all study materials. Each site must observe local policies and applicable state and federal regulations concerning study devices.

The device used in this study is the MagPro R30 Magnetic Stimulator, manufactured by Tonica Elektronik A/S.

2. RESPONSIBILITIES OF THE PARTICIPATING INVESTIGATOR

The SI at each site is responsible for:

2.1 Providing PCC with the following documents:

2.1.1 Investigator's Signed Agreement (ISA): The PCC will provide each SI with a partially completed "Investigator's Signed Agreement" form. This form must be completed, signed, and returned to the PCC prior to the shipment of any clinical trial devices to your center.

2.1.2 Curriculum Vitae: A signed and dated copy of the investigator's updated curriculum vitae (CV) must be attached to each "Investigator's Signed Agreement."

2.1.3 Research Committee Approval: A signed letter from the Associate Chief of Staff (ACOS) for Research and Development or other authorized individual indicating CSP #556 has been approved at your center. The letter must list the name of the SI who is responsible for the clinical trial. A copy of this document must be received before PCC will arrange shipment of the clinical trial device to your center.

2.2 Retaining all study-related documents until notified by the CSP Coordinating Center concerning the disposition of the documents. CSP studies remain active for five years after the last patient follow-up.

2.3 The SI, any subinvestigator, and any other personnel associated with the study will not represent that device used in CSP #556 is safe or effective for the purpose for which it is being investigated.

2.4 The site investigator will use the investigational device only with subjects under the investigator's personal supervision or under the supervision of a sub investigator listed on the Site Investigator's Agreement (SIA). The investigational device may be used only for the purpose of this study.

3. DESCRIPTION OF CLINICAL TRIAL DEVICES

3.1 Clinical Trial Device - The device used in this study is the MagPro R30 Magnetic Stimulator for repetitive transcranial magnetic stimulation (rTMS) in treating Treatment-Resistant Major Depression (TRMD). The device is programmed to (a) determine a patient's motor threshold and (b) deliver active or sham magnetic stimulation, depending the participant's treatment assignment. An Operator's Manual with instructions for the use of the MagPro R30 will be sent prior to the first randomization and will be available on the study SharePoint site.

4. CLINICAL TRIAL DEVICES AND CLINICAL TRIAL AIDS

4.1 RTMS device and associated equipment. Following receipt of all required documentation (Section 2.1), the PCC will arrange for shipment, installation, and training of the rTMS device by the manufacturer.

4.2 Audiometer. Following receipt of all required documentation the PCC will ship one Earscan 3 screening audiometer to each site. Each audiometer includes a manual which is also available at <http://www.earscan.com/earscan3m.aspx>.

4.3 Alcohol and drug test kits. Following receipt of all required documentation and in anticipation of imminent randomization, PCC will ship commercially-available drug and alcohol tests to each site. These will be used in participants as specified in the protocol. These tests must be stored at room temperature in a locked room. Directions for use are included with each test. To reorder, sites should contact PCC via email, fax or phone.

4.4 Patient ID Cards – PCC will ship patient identification (ID) cards to each site. At the randomization visit, this wallet-sized ID card should be filled out and given to the subject with instructions to present the card to any clinician seen for medical treatment while participating in CSP #556. If additional Patient ID cards are needed, the site coordinator should contact PCC via email, fax or phone.

CSP 556 Patient ID card (Printing on Both Sides of the Card)

CSP #556 PATIENT IDENTIFICATION CARD
 
Patient's Name _____ Address _____ Phone # _____ Subject ID #: _____ Subject Treatment #: _____
 
I am participating in a clinical trial being conducted at the _____ During this trial I will have repetitive transcranial magnetic stimulation (rTMS) or sham treatment that may decrease my depression symptoms. Please contact the physician or nurse listed on the backside of this card if I require medical attention that might be affected by my participation in this trial or if you have questions regarding the trial.
	
IN CASE OF EMERGENCY, Please Notify:
 
Site Investigator: _____ Name _____ Work number _____ Nurse: _____ Name _____ Work number _____
 
National Clinical Trial Chairs: [name]. [contact] [name]. [contact] J. [name]. [contact] [name]
 
Pharmacy Coordinating Center: [contact] (24 hrs/7 days per week) Study Biostatistician: [contact] [name]
 
This card should be shown to any health care professional treating you for any reason.

---	---

4.5 Electrodes. Following receipt of all required documentation and in anticipation of imminent randomization, PCC will ship two types of electrodes to each site. Stimulating electrodes will be used to mimic the sensation of active TMS. Recording electrodes will be used to evaluate motor threshold. See Operators Manual for complete information. If more electrodes are needed, sites should contact PCC by email, fax, or phone.

4.6 Ancillary supplies. PCC will provide all supplies listed on the table below once required documentation is received and sites are ready to start the study.

Supply	Description of use	Resupply
Fabric caps	Various sizes of fabric caps to be used for the correct placement of the rTMS coil.	Contact PCC
Styrofoam sheets	Boxes of Styrofoam sheets used to cushion a patients head from the rTMS coil	Not provided. If more sheets are needed, sites should order using their site budget.
Earphone covers	Disposable covers to place on the earphones of the audiometer for each patient use	Contact PCC

5. VERIFICATION OF rTMS DEVICE

Each device will be delivered to a site and tested for functionality by the MagVenture technicians. Each device will also be verified by PCC Quality Compliance personnel for performance of active and sham treatments.

